2.1 Source(s) of Support

Type/Source	Grant Title	Name of PI on Grant	Status
Federal Agency NIH/NCCIH	Neural Mechanisms of Mindfulness: a Discordant Twin Design	[name]	AWARDED
Attachment Name	Category	Version	Date Attached
1R21AT009483-01 [name] NCCIH JIT Letter.pdf compiled application.pdf	Notice of Just in Time (JIT) Documentation Grant from funding source or private foundation/association	1 1	01/17/17 01/17/17

3. Research Team

4.7 Does this project involve administration of recombinant DNA (gene therapy) or microorganisms?

No

4.8 Does this study involve the use of human embryonic stem cells or human induced pluripotent stem cells?

No

4.9 Does this study involve research in which a human embryo or embryos are destroyed, discarded, or knowingly subjected to risk of injury or death greater than that allowed for research on fetuses in utero?

No

4.10 Will a Certificate of confidentiality be used for this research?

No

4.11 Does this project need to be registered on ClinicalTrials.gov?

Yes

4.11.a Who is the Responsible Party for registering this study in ClinicalTrials.gov?

Principal Investigator

4.12 Title that should appear in Epic (and will be visible in the patient medical record):

N/A

4.13 Select one person from the study team that should appear in Epic as the contact person for this study:

[name]

4.14 Do you want to request that an ordering tool be built for your study in Epic?

No

4.15 Would you like to submit a request for the Epic team to consider your study for the use of BPA (Best Practice Advisory) in Epic?

No

4.16 Would you like to submit a request for the Epic team to build your questionnaires in Epic for the purposes of recruitment?

No

4.17 Will any external monitors require access to this study in Epic?

No

4.19 Mark all that apply to your study:

1. Protocol

1.1 Is there a separate, written protocol that will be submitted in addition to this form? (Note: a grant application is not considered to be a protocol)

No

1.2 Select up to three key words below that best describe this research study:

- Psychology
- Clinical

1.3 Provide a short summary/abstract of the purpose and procedures of the study proposed in this IRB application.

- DO NOT include information on studies not proposed in this application.
- Use LAY terminology only. This must be easily understandable by IRB community members and nonscientists.
- DO NOT cut and paste technical abstracts from source of support applications that may not be understood by a general audience.

This project focuses on understanding the cognitive and neural mechanisms by which mindfulness training (MT) results in positive behavioral change and enhanced psychological well-being. Building upon research by the Human Connectome project and the Dual Mechanisms of Cognitive Control studies, we will recruit MZ and DZ twins and non twin siblings, to participate in fMRI sessions.

The subjects will be recruited in pairs, with one subject randomly assigned to the MT condition (mindfulness-based stress reduction, or MBSR; the most-validated and standardized form of MT instruction) and the other serving as a (wait-list) control. Each co-subject will undergo extensive behavioral and MRI neuroimaging assessments in a pre/post fashion, before and after the MT (or no-contact control) intervention, to test for specific MT-related effects.

1.4 Specify your research question(s), study aims or hypotheses:

We will use this design to investigate theoretically-focused hypotheses that stem from our guiding framework regarding the neural mechanisms of cognitive control. Specifically, using a newly developed cognitive control task battery, we will test the counterintuitive hypothesis that MT produces an enhancement in the neural mechanism and circuits associated with reactive (rather than proactive) control. An additional subset of MZ twin participants will undergo retesting with the original HCP protocol, in order to provide a comprehensive assessment and comparison of MT effect sizes across multiple domains of cognitive and brain function. Success in this project will have high relevance for public health, by providing innovative experimental tools and a novel theoretical framework from which to empirically evaluate and better understand the potential impact of MT programs as lifestyle interventions for enhancing psychological well-being in healthy populations.

1.5 Background and significance and/or Preliminary studies related to this project:

Over the last decade, current understanding of the neural basis of complex psychological functions has shifted in emphasis from a focus on specific regions, to that of brain networks, while still highlighting the importance of key nodes within these networks. In terms of attentional and cognitive control, the lateral frontoparietal network(FPN) is generally agreed to be paramount. Within the FPN, dorsolateral prefrontal cortex (dIPFC) regions appear to function as critical hub nodes.

Strikingly, current cognitive neuroscience research has also associated MT with critical changes to each of these networks and key nodes. The FPN, and dIPFC in particular, show MT-related effects that appear to reflect both the state-changes associated with increased focusing of attention during meditative states, as well as potentially trait-related changes due to MT experience that result in more effective utilization of this network during attentional control tasks.

Building upon MZ and DZ research conducted by the HCP and current R37 study on dual mechanisms of cognitive control by [name], we will utilize the tasks and build upon the data of these successful and ongoing studies.

1.6 Literature cited/references (if attaching a grant enter N/A):

N/A

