1.20 What have you done to minimize any risks?

- No foreseeable risks

1.21 What are the potential benefits related to this project for:

- the participant (if any)
- benefits to society (if any)

There are no direct benefits to participants in this study.

This project has high relevance for public health by providing a rigorous and comprehensive evaluation of the effects of mindfulness training on psychological and brain function in healthy young adults. Although mindfulness practices are rapidly gaining in popularity as a lifestyle intervention to enhance psychological health and well-being, the brain basis of their effects are still not well-understood, particularly in healthy populations. The knowledge gained from this project will promote greater understanding and more informed decision-making regarding the potential benefits to be gained from instruction and training in mindfulness.

1.22 Provide a summary of the analysis methods you will use, including, if applicable, the data points or outcomes you will analyze.

Standard statistical analyses using a within subjects factorial ANOVA, t-test or regression. All data points will be included, which include experimental conditions (e.g., delay, target location). Dependent measure will be saccade accuracy.

1.23 Provide the rationale or power analysis to support the number of participants proposed to complete this study.

Estimates of power for all of our primary analyses are over 80% power to detect a medium or even small effect size with the proposed sample size. We are looking for extremely subtle effects in the data, including time-dependent changes in accuracy.

1.25 Will any data from this project be stored for use in future research studies?

Yes - contribution for future use is mandatory for participation in the study

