2.1 Will there be any adult participants?

Yes

2.1.a How many adult participants do you expect to consent or enroll under a waiver for this project?

50

2.1.b What is the age of the youngest adult participant?

18.0

2.1.c What is the age of the oldest adult participant?

45.0

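### Are at most 25 pairs too few, and the analysis in 1.22 unsuited, for the comparison of training effects across domains promised in 1.4?

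*Protocol*

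**What the plan says.** Protocol 1.4 sets the main hypothesis on reactive versus proactive control, tested with the four-task battery. It then adds a second strand: "An additional subset of MZ twin participants will undergo retesting with the original HCP protocol". The purpose given for this strand is to "provide a comprehensive assessment and comparison of MT effect sizes across multiple domains of cognitive and brain function". No size is given for the subset.

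The other relevant statements in the Protocol are:

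- 1.3 describes the population ("we will recruit MZ and DZ twins and non twin siblings, to participate in fMRI sessions"), the allocation ("The subjects will be recruited in pairs, with one subject randomly assigned to the MT condition") and the timing ("Each co-subject will undergo extensive behavioral and MRI neuroimaging assessments in a pre/post fashion").
- 1.5 says of the HCP and the earlier cognitive-control study that "we will utilize the tasks and build upon the data of these successful and ongoing studies".
- 1.13 describes the four-task sessions before and after the course. It describes no HCP session. Participants from the earlier cognitive-control study skip Sessions I and II.
- 1.22 names a within-subjects factorial ANOVA, a t-test or regression, without an effect-size metric.
- 1.23 states: "Estimates of power for all of our primary analyses are over 80% power to detect a medium or even small effect size".
- 2.1.a asks "How many adult participants do you expect to consent or enroll under a waiver for this project" and is answered 50.

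**The concern.** A difference between two effects is harder to estimate than either effect alone, unless the two are strongly correlated. Twenty-five pairs is a ceiling shared by MZ twins, DZ twins and non-twin siblings, and the HCP retest takes only a subset of the MZ pairs. If the team ranked domains by their training effects from so few pairs, much of the ranking could be noise.

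Two further worries come with this:

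- **Scale.** The word retesting, the reliance on existing data in 1.5 and the absence of a pre-training HCP session in 1.13 all suggest that the HCP baseline is an old visit. A within-subject standardised effect shrinks as the pre-post correlation falls, so equal training effects could look smaller in the HCP domains than in the four tasks.
- **Count.** An additional subset might be separate pairs inside the 50, which would take pairs from the main contrast, or extra pairs on top, which would make 50 too low.

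**Working it through.** **Inputs.** From the Protocol: 50 adults (2.1.a) in pairs (1.3), so 50 / 2 = 25 pairs at most. Assumed, because the Protocol does not give them: two-sided 5%, no dropout, medium effect 0.5 and small effect 0.2, and correlation ρ between two domains' pair differences from 0 to 0.6.

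**The plan's own figure.** Section 1.23 states over 80% power for a medium or even small effect. A paired t-test with 25 pairs (noncentral t) has 67% power at 0.5 SD of the pair difference and 16% at 0.2. Treating all 50 people as one within-subject group gives 93% and 28%. The figure is therefore reached for a medium effect only under favourable choices, and for a small effect in neither case. That is a question about 1.23 and the primary analyses. Section 1.23 gives no figure for the HCP comparison.

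**Difference between two domain effects.** Scale each domain's trained-minus-control pair difference to SD 1. The contrast then has SD = √(2(1−ρ)). The 95% half-width is t × SD / √n, with t = 2.064 for n = 25. The difference detectable with 80% power is 0.584 × SD, where 0.584 is the one-sample value for n = 25.

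| ρ | SD of contrast | Half-width, 25 pairs | Detectable, 25 pairs | Pairs needed for 0.5 SD |
|---|---|---|---|---|
| 0 | 1.414 | 0.58 | 0.83 | 65 |
| 0.3 | 1.183 | 0.49 | 0.69 | 46 |
| 0.6 | 0.894 | 0.37 | 0.52 | 28 |
| 0.7 | 0.775 | 0.32 | 0.45 | 21 |

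With 10 pairs and ρ = 0.3 the half-width is 2.262 × 1.183 / √10 = 0.85 SD.

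**The same question on a baseline-adjusted scale.** Express effects in between-person SDs and adjust the post-training pair difference for the earlier one. Assume a co-twin correlation of 0.5, a retest correlation of 0.5 and a cross-twin cross-time correlation of 0.3.

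- Variance of the pair difference at each time: 2(1 − 0.5) = 1.0.
- Covariance between the two times: 2(0.5 − 0.3) = 0.4.
- Residual variance: 1 − 0.4² = 0.84.

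The contrast SD is now √(0.84 × 2(1−ρ)). For a 0.5 SD difference with 80% power this needs 55, 39 and 24 pairs at ρ = 0, 0.3 and 0.6. The last lies within the 25.

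**Scale.** With r the pre-post correlation and uncorrelated co-twin changes, the pair difference in change has variance 4(1−r). A 0.5 SD effect then reads 0.5/√0.8 = 0.56 at r = 0.8 and 0.5/√2.0 = 0.35 at r = 0.5, which is 37% smaller. Both values of r are assumptions. The comparison also assumes that only the HCP baseline is old. Participants from the earlier study skip Sessions I and II under 1.13, so their four-task baseline is also earlier and undated.

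**Count.** If pairs were diverted from the four-task contrast, power at 0.5 SD of the pair difference would fall from 67% (25 pairs) to 56% (20) or 44% (15). Nothing in the Protocol says that any pair leaves that contrast.

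**The case for a change.** The strongest case for a change is that comparing effect sizes is the only purpose 1.4 gives for the HCP retest. Section 1.1 says that no separate protocol exists, so the form is the design document. Twenty-five is reached only if every pair is MZ and the subset is everyone. In unadjusted units, no correlation from 0 to 0.6 brings the requirement for a 0.5 SD difference down to 25 pairs. With 15 pairs, even ρ = 0.7 detects only 0.60 SD. Adding text on the subset and on interval reporting would cost almost nothing.

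The imprecision stands, and so does the missing description. The rest does not carry a change:

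- **Aim.** Section 1.4 states no test, ranking, equality claim or target difference. Recasting the retest as estimation would largely repeat what it already says.
- **Power.** Section 1.23 is limited to primary analyses, and the HCP retest is not called one.
- **Method.** Section 1.22 lists regression beside ANOVA and the t-test. Regression of the post-training pair difference on the earlier one is the adjustment that a common scale would use. Choosing the metric is ordinary SAP content.
- **Count.** A subset of the MZ twin participants reads most naturally as enrolled pairs who do an extra retest, although the word additional leaves some doubt. Section 2.1 (Source(s) of Support) lists an attached grant application, which may give the number; it is not available here.

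**Conclusion.** No change to the plan follows. The comparison across domains will be imprecise: a 95% half-width of 0.37 to 0.58 SD with all 25 pairs at assumed correlations of 0.6 to 0, and wider in a smaller subset. This misses no figure in the Protocol, since none is set for the comparison. Nor is it shown that 25 pairs cannot resolve a moderate difference. The answer turns on correlations and a target difference that the Protocol does not give, and on the adjusted scale 24 pairs suffice at ρ = 0.6.

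The scale problem is not established either. The old HCP baseline is inferred, no metric is fixed, and the 37% figure rests on two assumed pre-post correlations.

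The residue is a gap in description: the subset's size, whether it lies within the 50, and its HCP visits. A sensible team would count it inside the 50, keep those pairs in the four-task contrast, and report each domain's effect with its interval on a common scale without ranking the domains. Going further would mean enrolling more pairs for a test that the Protocol does not promise.

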1.7 Describe EACH of your participant populations

- Include description of any control group(s)
- Specify the Inclusion/Exclusion criteria for EACH group

Participants are healthy young adults of age range 18 to 45 years, native English speakers with no contraindication for fMRI.

We will recruit a cohort of monozygotic (MZ) and dizygotic twins and siblings from Missouri family registries. We will target individuals that have completed study 201510077, Dual Mechanisms of Cognitive Control.

Any participant will be excluded for the following reasons: 1) taking any medication with potential cognitive effects (e.g., sleeping pills); 2) taking any psychotropic medications; 3) the presence of any clinically unstable medical disorder, or a medical disorder that affects cognitive or motor function (e.g., epilepsy, Parkinson's Disease); and 4) present or past head injury with documented neurological sequelae, and/or causing loss of consciousness. Additionally, subjects for the fMRI studies will also be excluded for: 1) pregnancy; 2) history of claustrophobia; 3) non-medically approved metallic objects in the body; and 4) history of heart rhythm abnormalities or presence of a heart pacemaker.

In addition, we will screen for premature births (for twin pairs, before 34 weeks; for other siblings, before 37 weeks, to avoid inclusion of individuals with atypical connectivity patterns resulting from very premature birth.

1.8 Check all materials/methods that will be used in recruiting participants:

- Telephone script
- Ads/Brochures/Posters/News Release/Fliers
- Email or letters
- Other Materials - prior participants in study 201510077 ([name], PI) Dual Mechanisms of Cognitive Control
- Existing Registry/database
 - Other Research Study - prior participants in study 201510077 ([name], PI) Dual Mechanisms of Cognitive Control
 - Other Existing Registry/database - Missouri Family Registry (twin database)
- Medical Records or Other PHI

Attachment Name	Category	Version	Date Attached
DMCC_MBSR_EMAIL.rtf	Recruitment: Other	1	05/02/17
priorparticipantflyer.rtf	Recruitment Materials: Ads/Brochures/Posters/News Release/Fliers	1	05/15/17
newparticipantemailflyer.rtf	Recruitment Materials: Ads/Brochures/Posters/News Release/Fliers	1	05/15/17

1.8.a List the individual data elements you will need to access/use from the patient or clinic records to identify potential participants for recruitment
For the telephone screen, we are generating PHI in the form of medical history and medications (see attached phone screen document).

1.8.b What is the plan for participant identifiers obtained to identify participants for recruitment?

Identifiers for those who do NOT enroll will be destroyed at the earliest opportunity, consistent with the conduct of the research (for example when recruitment and enrollment are completed.)

1.8.c Does the research team agree that the requested information will not be reused or disclosed to any other person or entity, except as required by law, for authorized oversight of the study, or for other research for which the use or disclosure of the requested information would be permitted by the HIPAA Privacy Rule?

Yes

1.9 Will you use a screening log or other record that would include information on people who do not consent to participate in the study?
No

1.10 Describe where the consent discussion will occur (check all that apply):

- Private room or area
- By phone

1.11 Participants and/or their legally authorized representative will have (check all that apply to the consent process and explain process in Question 1.12 below):

- As much time as they desire to consider enrolling in the study, including:
 - An opportunity to thoroughly review the consent materials with knowledgeable members of the research team, and with family and/or friends as appropriate
 - Sufficient time to have all of their questions answered

1.12 Provide a description of the enrollment and consent process in sequential order and address EACH of the bulleted points below:

- Describe each study population separately including control population
- Describe when recruitment and consent materials are used
- Indicate how much time individuals will have to consider participation
- Use THIRD person active voice. For example, "the principal investigator will identify potential participants, the study coordinator will discuss the study with participants over the telephone and schedule the first study visit, etc..."
- Describe the steps that will be taken by the research team to minimize the possibility of coercion or undue influence during the consent process

We will recruit healthy young adult twin pairs. We will utilize the Missouri Twin registries.

Email: An email will be sent to former DMCC participants about the study.

Phone screen: A member of the research team will provide participants with information about the study and required elements of consent over the telephone (see attached telephone screen) prior to obtaining verbal consent to participate in the initial screening elements of the study. The initial phone screen will include questions about inclusion and exclusion criteria and the MR safety screening form, to ensure that we do not recruit participants who are unable to safely complete MR scans. An appointment will be set up with eligible subjects if they choose to participate.

In Lab:

If a participant is deemed eligible and agree to participation in the study, an appointment is scheduled. Upon arrival in the lab, the participant will be consented by an engaged research team member using the approved consent form. Participants will be allowed ample time to read/review the consent form and to ask questions. Participants will then complete: an intake review form, an fMRI screening form, and a demographic form. If any contraindications or exclusion criteria, the participant will be withdrawn from the study and paid for their time. If the participant is found eligible, the experiment will begin.

We will take steps to minimize the possibility of coercion and/or undue influence during the consent process by reminding the participants that their participation is completely voluntary, and may be ended at any time for any reason.

All members of the research team will have completed human subjects and HIPAA training through Washington University before having participant contact.

1.13 Provide a detailed description in sequential order of the study procedures following the consent process - DO NOT cut and paste from the Consent Document.

Describe study populations separately if they will be participating in different procedures

DESCRIBE:

- Control populations, if applicable
- Any randomization, if applicable
- What participants will be asked to do/what happens in the study (in sequential order)
- The time period over which procedures will occur
- Long-term follow-up and how it occurs

SESSION I:

A. Intake: This will involve a brief interview and data on standard physiologic information (height, weight, blood pressure, and pulse). If blood pressure is considered high, participant will be given an information sheet at the end of their session. All participants will then be administered the MRI screening form and demographic form. If participant is deemed eligible, the experiment will commence. If they are ineligible, they will be told why and will be withdrawn from the study.

B. Behavioral Practice Session (This will take approximately 2 hours.)

1. TASKS: Participant will complete 4 behavioral tasks (AXCPT, Stroop, Sternberg and Taskswitching) on a computer. Subjects will complete the Operational and Symmetry Span tasks, an 18 item Ravens Matrices task, a breath counting task, and a Letter Set task.

2. Questionnaires:

Subjects will also complete behavioral questionnaires during practice sessions, which include: Behavioral Inhibition System/Behavioral Approach System (BIS/BAS)

Need for Cognition Scale (Nfc)

Generalized Reward and Punishment Expectancy Scales (GRAPES)

Mindful Attention Awareness Scale (MAAS)

Five Facet Mindfulness Questionnaire (FFMQ)

Pittsburgh Sleep Quality Index

State Trait Anxiety Inventory (STAI)

Domain Specific Risk Taking(DOSPERT)

The Positive and Negative Affect Schedule(PANAS)

Sensitivity to Reward and Punishment Questionnaire

Self-Scoring Self Control Scale (SSC)

Barratt Impulsiveness Scale (BIS)

Alcohol&Smoking Questionnaire

Neo FFI

Fordyce

Patient health questionnaire (PHQ0

Satisfaction with Life (SWL)

Self Compassion scale (scmp)

Pittsburgh sleep quality index (PSQI)

Exit Satisfaction Survey

pre & post task questionnaires

C. Break

D. Scanning: In the scanner, participants will perform baseline session of the 4 tasks (AXCPT, Stroop, Task-switching and Sternberg) in a scanner. This will take approximately 2 hours. Blood pressure and pulse will be measured prior to scan. Scanning will consist of structural, functional and resting state acquisition.

E. Review of schedule for Scanning Session II.

Session II and Session III (can either be completed on the same day or broken into two sessions A&B&D, A,C,D):

A. Behavioral Practice Session: Participant will complete 4 behavioral tasks (AXCPT, Stroop, Sternberg and Task-switching) on a computer. Participants will practice the corresponding (counterbalanced order of proactive/reactive) condition of the tasks outside of the scanner before the scanning sessions. These practice sessions will last approximately 30 minutes each. If not completed, subjects will complete any questionnaires remaining from Session I Behavioral Practice.

B. Scanning Sessions:

Participant will perform two scanning sessions in Session II of the study. The sessions will be counterbalanced between the proactive and reactive conditions of the four tasks (AXCPT, Stroop, Task-switching and Sternberg) in a scanner. Scanning will consist of both functional (tasks) and resting state acquisition. Each scan will last approximately two hours. Blood pressure and pulse will be measured prior to the scan.

B: Break

C. Second Scanning Session (of counterbalance)

D. Exit Survey (post-task questionnaire)/Debriefing

One of the twin participants will be randomly selected to participate in an 8-week Mindfulness-based stress reduction (MBSR) program led by certified MBSR instructors at a dedicated facility, supervised by [name]. The MBSR program uses a combination of mindfulness meditation, body awareness, and yoga to help people become more mindful. The MBSR program is an eight-week workshop taught by certified trainers that entails weekly group meetings (two-hour classes) and a one-day retreat (six-hour mindfulness practice) between sessions six and seven, home practice, and instruction in three formal techniques: mindfulness meditation, body awareness, and simple yoga posture.

After the completion of the program, the twins will return for sessions three and four - a repeat/retest of Session I and II.

If participants that have completed or are enrolled in IRB 201510077, Dual Mechanisms of Cognitive Control ([name], PI), they will not complete session one and two. They will be asked to begin at the mindfulness training and complete sessions three and four.

The twin that was not chosen to participate in the MBSR initially will be given the opportunity to voluntarily participate after the completion of the retest sessions.

Task descriptions:

AXCPT:

In the AXCPT task, a modified version of the continuous performance task, participants are told to make one response for the letter X when it was preceded by the letter A, and another response for all other stimuli. AX trials are "target trials"; in these types of trials a valid cue is followed by a valid probe. The 3 other trial types are "Nontarget trials" in which either a valid cue is followed by an invalid probe ("AY" type trials) or an invalid cue is followed by either a valid or invalid probe ("BX" or "BY" probes, respectively). Participants will be asked to respond by pushing a button. The baseline, proactive and reactive versions of the task will vary the number of AX, AY and BX and BY trials.

Sternberg:

In the Sternberg task, participants will be shown word lists on a computer monitor and will be asked to make judgments about them by pushing buttons. During each trial, participants will observe presentation of a list of items to memorize, followed by a memory maintenance period during which the subject must maintain the list of items in memory. The maintenance period is terminated by the onset of a 'probe' letter, to which the subject must respond whether the item was in their memorized list of items or not. Participants will be asked to decide if the probe word appeared in the lists within the trial indicating yes or no via a button press. The baseline, proactive and reactive variants of the task will vary in the length of the word lists, i.e. short list 23 words, medium list 45 words, long list 67 words. The baseline, proactive and reactive conditions will vary the load and frequency of the lists.

Stroop:

In a Stroop task, participants name the color of ink a word is printed in (e.g., RED in blue ink [incongruent] or RED in red ink [congruent]) or the picture of an animal while ignoring a word (e.g., cat picture with word FISH superimposed [incongruent] or cat picture with word CAT superimposed [congruent]). Responses will be recorded as an audio .wav file

During the behavioral and the scanning session, each participant will complete 3 versions of the task as follows:

The baseline variant of this task will involve the presentation of mostly congruent items.

The proactive variant will involve the administration of mostly incongruent items, and the reactive version will involve the administration of 50% congruent items.

The reactive version, half of the items (e.g., the words RED and BLUE or the pictures cat and fish) will be mostly congruent and the other half will be mostly incongruent, which is referred to as an item-specific variation.

Participants will be asked to respond aloud, with their voice used to mark reaction time. A recorded file will also be saved, de-identified and stored, to later record accuracy.

TaskSwitching:

In a task-switching task, participants are cued as to which of two tasks are relevant for a given trial, and are asked to respond to the stimuli following the cue. The two tasks that may be cued involved simple judgments such as vowel/consonant judgment (e.g., is E a vowel or consonant, digit judgment (e.g., is 3 smaller or larger than 5), word judgment (e.g., how many syllable in TORCH, or does the word refer to an object that is smaller or larger than a basketball), or picture judgment (e.g., does the picture reflect a mode of transportation that involves car/plane or bike/boat? In a mixed task block, both tasks are relevant and can be cued on a given trial, and sometimes one task is cued more frequently than the other. In a single task block, only one task is relevant at a time (i.e., can be cued). Participants respond by pressing designated keys on a keyboard. Reaction time and accuracy are recorded.

The baseline, proactive and reactive variants will involve intervals of varying length between stimuli and congruency.

Incentives (i.e., a cue indicating a trial is worth more points or other incentive) may be added to encourage proactive preparation of the cued task.

Span Tasks:

Operational Span Task: measures general capacity for working memory. In this task, participants are asked to read and verify a simple math problem and then read a word after the operation (such as SNOW). After a series of problems and words has been presented, the participants recall the words that followed each operation. The number of operation word

strings in a sequence is increased and decreased to measure the participant's operation span. Operation span measures predict verbal abilities and reading comprehension even though the subjects are solving mathematical problems.

Symmetry Span tasks: The Symmetry span task is a complex span partner to the matrix span task. The participant is shown a series of grid locations onebyone form the 4x4 grid in the center of the screen. The participant must remember the grids and the order in which they appeared. After each grid is shown the participant is shown an 8x8 grid that has a number of grids filled black to form a pattern. The pattern will either be symmetrical along the vertical axis or it will not and the participant must make this judgement using the left/right arrow keys before the next grid will be shown.

18 item Ravens Matrices: a nonverbal group test typically used in educational settings. It is usually a 60item test used in measuring abstract reasoning and regarded as a nonverbal estimate of fluid intelligence

Letter Set task: presents series of letters in a pattern. Subject responds to which does or does not fit the pattern. This task is used as a measure of fluid intelligence.

Breath Counting task: Participants press a key for each exhale for breaths 1-8 and a separate key for 9 breath, then reset. If they lose track of breaths, they press a 3rd reset key.

Questionnaires:

1. Behavioral Inhibition System/Behavioral Approach System (BIS/BAS): A behavioral approach system (BAS) is believed to regulate appetitive motives, in which the goal is to move toward something desired. A behavioral avoidance (or inhibition) system (BIS) is said to regulate aversive motives, in which the goal is to move away from something unpleasant. We developed the BIS/BAS scales to assess individual differences in the sensitivity of these systems.
2. The Need for Cognition Scale is an assessment instrument that quantitatively measures "the tendency for an individual to engage in and enjoy thinking" (Cacioppo & Petty, 1982, p. 116). The Need for Cognition Scale asks individuals to rate the extent to which they agree with statements about the satisfaction they gain from thinking.
3. Generalized Reward and Punishment Expectancy Scales (GRAPES): A scale to assess generalized reward and punishments expectancies in individuals.
4. Mindfulness Attention Awareness Scale (MAAS): The trait MAAS is a 15item scale designed to assess a core characteristic of mindfulness, namely, a receptive state of mind in which attention, informed by a sensitive awareness of what is occurring in the present, simply observes what is taking place.
5. Five Facet Mindfulness Questionnaire (FFMQ): This instrument is based on a factor analytic study of five independently developed mindfulness questionnaires. The analysis yielded five factors that appear to represent elements of mindfulness as it is currently conceptualized. The five facets are observing, describing, acting with awareness, non-judging of inner experience, and non-reactivity to inner experience.
6. State Trait Anxiety Inventory (STAI): is a commonly used measure of trait and state anxiety at both poles of the normal affect curve (state vs. trait).
7. DomainSpecific RiskTaking (DOSPERT) is a psychometric scale that assesses risk taking in five content domains: financial decisions (separately for investing versus gambling), health/safety, recreational, ethical, and social decisions.
8. Self Scoring Self Control Scale (SCC): Measures self control.
9. The Positive and Negative Affect Schedule(PANAS: The Positive and Negative Affect Schedule (PANAS) comprises two mood scales, one that measures positive affect and the other which measures negative affect. Used as a psychometric scale, the PANAS can show relations between positive and negative affect with personality traits and traits. Ten descriptors are used for each PA scale and NA to define their meanings.
10. Sensitivity to Reward and Punishment Questionnaire: The Sensitivity to Punishment and Sensitivity to Reward Questionnaire (SPSRQ) has been proposed as a measure of the behavioral approach system (BAS) and behavioral inhibition system (BIS).
11. Barratt Impulsiveness Scale (BIS) The BIS was designed to assess the personality trait of impulsiveness. It was intended to be an improvement over previous versions of the BIS, including Barratt's (1959) original measure
13. Pittsburgh Sleep Quality Index (PSQI: The Pittsburgh Sleep Quality Index (PSQI) is an effective instrument used to measure the quality and patterns of sleep in the older adult. It differentiates "poor" from "good" sleep by measuring seven domains: subjective sleep quality, sleep latency, sleep duration, habitual sleep efficiency, sleep disturbances, use of sleep medication, and daytime dysfunction over the last month.
14. Alcohol and Smoking: used to gauge alcohol and tobacco use in subjects. Results compared with individual difference measures.

